### 16.3 Statistical Design:

#### 16.31 Decision Rule:

Previous studies of evaluation of minimal residual disease in multiple myeloma have been limited and have included small numbers of patients. In one previous study of lenalidomide, bortezomib and dexamethasone (RVD) induction followed by ASCT followed by 2 cycles of RVD consolidation and 1-year Lenalidomide maintenance in 31 untreated transplant eligible MM patients, an MRD negative response rate of 54% by flow cytometry was seen post ASCT in 26 evaluable patients tested. A MRD negative response rate of 65% by bone marrow flow cytometry would be of interest for this study.

The largest success proportion where the proposed treatment regimen would be considered ineffective in this population is 45%, and the smallest success proportion that would warrant subsequent studies with the proposed regimen in this patient population is 65%. The following one-stage design with an interim analysis is based on a two-stage Simon optimum design and requires 45 evaluable patients to test the null hypothesis that the true success proportion in this patient population is at most 45%.

- 16.311 Interim Analysis: Enter 20 evaluable patients into the study. If 9 or fewer successes are observed in the first 20 evaluable patients, we will consider this regimen ineffective in this patient population and terminate the

study. Otherwise, if the number of successes is at least 10, we will continue accrual.

16.312 Final Decision Rule: Enter an additional 25 evaluable patients into the study. If 24 or fewer successes are observed in the first 45 evaluable patients, we will consider this regimen ineffective in this patient population and terminate this study. Otherwise, if the number of successes is at least 25, this will be considered evidence of promising activity and the treatment may be recommended for further testing in subsequent studies in this population.

16.313 Over Accrual: If more than the target number of patients are accrued, the additional patients will not be used to evaluate the stopping rule or used in any decision making process.

16.314 NOTE: We will not suspend accrual at the interim analysis to allow the first 20 patients to become evaluable, unless undue toxicity is observed. Given the limited overall sample size and the inclusion of an adverse events stopping rule, we feel it is ethical to not halt accrual for the interim analysis. However, if accrual is extremely rapid, we may temporarily suspend accrual in order to obtain safety data on these patients before re-opening accrual to further patients.

16.32 Power and Significance Level: Assuming that the number of successes is binomially distributed, the significance level is .09, i.e. there is a 9% chance of finding the drug to be effective when it truly is not. The probability of declaring that this regimen warrants further study (i.e. statistical power) and the probability of stopping at the interim analysis under various success proportions can be tabulated as a function of the true success proportion as shown in the following table.

If the true success proportion is...	0.45	0.50	0.55	0.60	0.65
Then the probability of declaring that the regimen warrants further study is...	0.09	0.25	0.49	0.74	0.90
And the probability of stopping at the interim analysis is...	0.59	0.41	0.25	0.13	0.05

16.33 Other considerations: Adverse events, quality/duration of response, and patterns of treatment failure observed in this study, as well as scientific discoveries or changes in standard care will be taken into account in any decision to terminate the study.

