## 16.0 Statistical Considerations and Methodology

### 16.1 Overview

This is a phase II study of Daratumumab for transplant eligible multiple myeloma patients. This study is designed to assess the rate of minimal residual disease (MRD) negativity using a one stage phase II study design with an interim analysis in patients with transplant eligible multiple myeloma.

- 16.11 Primary Endpoint: The primary endpoint of this study is the rate of MRD negative response after ASCT. MRD negative response after ASCT is defined as achievement of MRD negative status in the bone marrow by flow cytometry (MPF) at the day 100 post ASCT visit. All patients meeting the eligibility criteria, who have signed a consent form and have begun treatment will be evaluable for response, unless they are determined to be a major violation.
- 16.12 Sample Size: The one stage study design with an interim analysis to be used is fully described below. A minimum of 20 and a maximum of 45 evaluable patients will be accrued total onto this phase II study unless undue toxicity is encountered. We anticipate accruing an additional 5 patients to account for ineligibility, cancellation, major treatment violation, or other reasons for a total of 50 patients overall.
- 16.13 Accrual Rate and Study Duration: The anticipated accrual rate is 2 evaluable multiple myeloma patients per month. Therefore, the accrual period for this phase II study is expected to be about 2 years. The maximum total study duration is expected to be approximately 5 years, or until the last patient accrued has been observed at least for 3 years after registration.

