#### 16.4 Analysis Plan

The analysis for this trial will commence at planned time points (see 16.2) and at the time the patients have become evaluable for the primary endpoint. The Statistician and Study Chair will make the decision, in accord with CCS Standard Operating Procedures, availability of data for secondary endpoints (e.g., laboratory correlates), and the level of data maturity. It is anticipated that the earliest date in which the results will be made available via manuscript, abstract, or presentation format is all patients have been

followed at least through the day 100 post ASCT visit (approximately 8 months) or have discontinued study treatment prior to ASCT.

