#### 16.41 Primary Outcome Analysis:

16.411 Definition: The primary endpoint of this trial is the rate of MRD negative response after ASCT. MRD negative response after ASCT is defined as achievement of MRD negative status in the bone marrow by flow cytometry (MPF) at the day 100 post ASCT visit. All patients meeting the eligibility criteria who have signed a consent form and have begun treatment will be evaluable for response, unless they are determined to be a major violation.

16.412 Estimation: The proportion of successes will be estimated by the number of successes divided by the total number of evaluable patients. Ninety-five percent confidence intervals for the true success proportion will be calculated according to the approach of Duffy and Santner.

16.413 Over Accrual: If more than the target number of patients are accrued, the additional patients will not be used to evaluate the stopping rule or used in any decision making processes; however, they will be included in final point estimates and confidence intervals

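### Section 16.311 could close accrual at the 11th confirmed non-success among the first 20: the same decision and error rates, and on average 2.7 fewer patients per futility stop at a true rate of 45%

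*Combined protocol and SAP*

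**What the plan says.** Section 16.311 sets the futility rule: the regimen is judged ineffective and the study ends "If 9 or fewer successes are observed in the first 20 evaluable patients". With 10 or more successes, 16.312 continues: "Enter an additional 25 evaluable patients into the study".

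Section 16.314 keeps enrolment open during the wait: "We will not suspend accrual at the interim analysis to allow the first 20 patients to become evaluable, unless undue toxicity is observed". It gives its reason: "Given the limited overall sample size and the inclusion of an adverse events stopping rule, we feel it is ethical to not halt accrual". It also allows a temporary suspension if accrual is extremely rapid.

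Three other statements fix the timing and the denominator:
- 16.13: "The anticipated accrual rate is 2 evaluable multiple myeloma patients per month".
- 16.4: results are expected once all patients have been "followed at least through the day 100 post ASCT visit (approximately 8 months) or have discontinued study treatment prior to ASCT".
- 16.411: "All patients meeting the eligibility criteria who have signed a consent form and have begun treatment will be evaluable for response", major violations excepted. Section 16.412 divides successes by all evaluable patients.

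Section 16.12 gives the size as "A minimum of 20 and a maximum of 45 evaluable patients will be accrued total onto this phase II study". Section 16.33 lets patterns of treatment failure, among other things, inform a decision to end the study. Section 16.51 has the investigators and statistician review the study at least twice a year. No section says what happens when 11 non-successes have been recorded among the first 20.

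**The concern.** The primary endpoint is read about 8 months after registration while patients enter at 2 a month, so most of the second stage is already enrolled when the interim count is complete. That follows from a disclosed choice in 16.314. The narrower issue is that the count is often decided before it is complete. After the 11th non-success the futility boundary must be crossed, whatever the remaining results show. The ethical argument in 16.314 supports enrolling while the answer is unknown; it does not address enrolling after the answer is fixed. At a true rate of 45% the futility stop is the more likely outcome (0.59), so the situation is not remote. At stake are a few patients entering a regimen that the plan's own rule is bound to call ineffective.

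**Working it through.** **Inputs.** Boundaries 9/20 and 24/45 (16.311, 16.312); true rates 0.45 to 0.65 (16.32); 2 evaluable patients a month (16.13); about 8 months to Day 100 (16.4); the windows in 6.15, 7.11 and 7.12.

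**1. The plan's table.** With X ~ Bin(20, p) and Y ~ Bin(25, p):
- P(stop) = P(X ≤ 9)
- P(promising) = Σ over x = 10..20 of P(X = x) · P(Y ≥ 25 − x)

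At p = 0.45, 0.50, 0.55, 0.60, 0.65 these give P(stop) = 0.591, 0.412, 0.249, 0.128, 0.053 and P(promising) = 0.090, 0.249, 0.491, 0.735, 0.900. Every cell agrees with 16.32 after rounding.

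**2. Accrued when all 20 are read.** Patients accrued = 20 + 2 × lag in months.
- Plan's figure: 20 + 2 × 8 = 36, leaving 45 − 36 = 9 patients spared by a stop.
- Shortest path: 28 + 28 + 90 = 146 days = 4.8 months, giving 29.6 (15.4 spared).
- Longest path: 28 days to start, three 28-day cycles (84), a last cycle of up to 84 days, then 110 = 306 days = 10.05 months, giving 40.1 (4.9 spared).

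This range holds the rate at 2 a month. At 1 a month and 8 months the figure is 20 + 8 = 28.

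**3. Same event.** Eleven or more non-successes in 20 is the same as 9 or fewer successes in 20. Let K be the position of the 11th non-success: P(K = k) = C(k − 1, 10) · (1 − p)^11 · p^(k − 11). Summed over k = 11..20 this gives 0.5914 at p = 0.45 and 0.0532 at p = 0.65, identical to step 1. Alpha (0.0903) and power (0.9001) therefore do not move.

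**4. Gain, given a stop at p = 0.45.** E[K | K ≤ 20] = 17.3. With an 8-month lag, accrual ends at 17.3 + 16 = 33.3 instead of 36, a mean of 2.7 fewer. P(K ≤ 17 | stop) = 0.491, so 3 or more are spared in 49% of stops. P(K = 20 | stop) = 0.165 to three decimals (0.1647), so none are spared in 16%. The stop is certain before the 20th patient in the other 84%.

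**5. Gain over all trials, 8-month lag.** Expected accrual as written is 45 − 9 · P(stop). The trigger subtracts a further P(stop) × (mean gain per stop).

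| True rate | P(stop) | Mean gain per stop | Gain over all trials | Expected accrual |
|---|---|---|---|---|
| 0.45 | 0.591 | 2.7 | 1.6 | 39.7 to 38.1 |
| 0.50 | 0.412 | 2.3 | 0.9 | 41.3 to 40.4 |
| 0.55 | 0.249 | 1.9 | 0.5 | 42.8 to 42.3 |
| 0.65 | 0.053 | 1.5 | 0.1 | 44.5 to 44.4 |

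**6. Sensitivity at p = 0.45.** With a constant lag the gain per stop stays at 2.7 whether the lag is 5, 8 or 10 months. If individual timings are assumed uniform over the protocol windows, with 0%, 20% or 50% of patients on optional cycles 3 and 4, mean accrual when the slowest of the 20 is read is 33, 34 or 36, and the trigger lowers expected accrual by 1.8 to 2.1.

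**The case against.** The strongest case against is that nothing here is wrong. The design is standard, its table is correct, and 16.314 discloses and justifies open accrual. All of that stands, and it is why this is an optional improvement.

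A reader might infer that 16.311 obliges the team to wait for all 20 results. It does not: it states a condition on the first 20, and that condition is settled at the 11th non-success. Section 16.33 also leaves room to stop on accumulating failures. What is missing is a trigger, since 16.33 is discretionary and 16.51 guarantees review only twice a year.

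A reader might also infer that the minimum of 20 in 16.12 is wrong, or that open accrual disturbs the error rates. Neither is supported: 20 is a valid lower bound, and the interim decision uses only the first 20 evaluable patients.

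It is fair to say that a saving of about 3 patients is the favourable case. It needs both a stop and a true rate near 45%, and even then 51% of stops spare two or fewer.

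The objection with most practical force is that a non-success is not fully defined. Section 16.411 asks only for flow MRD negativity at Day 100, whereas Table 11.5 footnote k makes flow MRD negativity conditional on complete response. Patients who leave before ASCT stay in the denominator, but their outcome is not stated. The 9/20 rule has the same gap, though a trigger acting on a single event makes it more visible.

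**Conclusion.** The point holds as a minor improvement. An explicit stop at the 11th confirmed non-success reaches the same decision with the same alpha, power and stopping probabilities, and closes accrual sooner in 84% of futility stops at a true rate of 45%. The mean gain there is 2.7 patients per stop and 1.6 over all trials, shrinking quickly as the true rate rises. It does not remove the overrun: about 33 of 45 patients would still be accrued at a stop, because that comes from the lag with accrual open.

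The figures rest on 2 evaluable patients a month, an 8-month lag common to all patients, and non-successes counted as each result arrives. They count evaluable patients, not registrations.

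**What to change.** Add to 16.311 that accrual closes as soon as 11 of the first 20 evaluable patients, by order of entry, are confirmed non-successes, with these provisions:

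- **Status check.** Before closing, confirm that none of the 11 is ineligible (13.5) or a major violation (13.6). Major violation concerns cycle 1, so it can be settled before Day 100. Section 13.5 sets no deadline for finding ineligibility, so the check must be made actively. Later exclusion of any of the other nine cannot reverse the stop: it brings later patients into the first 20 and pushes no counted patient out.
- **Definition.** Judge non-success by the same success definition as the 9/20 rule, and include evaluable patients who can no longer have the Day 100 assessment, since 16.411 and 16.412 keep them in the denominator.
- **Footnote k.** State, for both rules, whether the complete-response requirement in Table 11.5 applies to the 16.411 endpoint.

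The cost is a few sentences and rolling work: Day 100 results and pre-ASCT discontinuations among the first 20 must be counted and checked as they occur, not only at the twice-yearly review. No extra patients or assessments are needed. The change concerns accrual only and says nothing about the treatment of patients already enrolled.

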#### 16.4 Analysis Plan

The analysis for this trial will commence at planned time points (see 16.2) and at the time the patients have become evaluable for the primary endpoint. The Statistician and Study Chair will make the decision, in accord with CCS Standard Operating Procedures, availability of data for secondary endpoints (e.g., laboratory correlates), and the level of data maturity. It is anticipated that the earliest date in which the results will be made available via manuscript, abstract, or presentation format is all patients have been

followed at least through the day 100 post ASCT visit (approximately 8 months) or have discontinued study treatment prior to ASCT.

#### 16.41 Primary Outcome Analysis:

16.411 Definition: The primary endpoint of this trial is the rate of MRD negative response after ASCT. MRD negative response after ASCT is defined as achievement of MRD negative status in the bone marrow by flow cytometry (MPF) at the day 100 post ASCT visit. All patients meeting the eligibility criteria who have signed a consent form and have begun treatment will be evaluable for response, unless they are determined to be a major violation.

16.412 Estimation: The proportion of successes will be estimated by the number of successes divided by the total number of evaluable patients. Ninety-five percent confidence intervals for the true success proportion will be calculated according to the approach of Duffy and Santner.

16.413 Over Accrual: If more than the target number of patients are accrued, the additional patients will not be used to evaluate the stopping rule or used in any decision making processes; however, they will be included in final point estimates and confidence intervals

#### 16.42 Secondary Outcome Analyses

The rate of MRD negative response after pre-SCT consolidation with Daratumumab will be estimated by the number of patients who achieve MRD negative status by flow cytometry (MPF) in the bone marrow after pre-SCT consolidation with Daratumumab divided by the total number of evaluable patients. Exact binomial 95% confidence intervals for the true rate of MRD negative response after pre-SCT consolidation with Daratumumab will be calculated.

The rate of MRD negative response after 1 year (12 cycles) of Daratumumab and lenalidomide maintenance will be estimated by the number of patients who achieve MRD negative status by flow cytometry (MPF) in the bone marrow after 1 year of maintenance therapy divided by the total number of evaluable patients. Exact binomial 95% confidence intervals for the true rate of MRD negative response after 1 year of maintenance will be calculated.

Progression-free survival time is defined as the time from registration to the time of progression or death due to any cause. Patients who are alive and progression-free will be censored on the date of their last disease assessment. Patients who receive subsequent treatment for myeloma before disease progression will be censored on the date of their last disease assessment prior to initiation of the subsequent treatment. The distribution of progression-free survival will be estimated using the method of Kaplan-Meier.

Survival time is defined as the time from registration to death due to any cause. The distribution of survival time will be estimated using the method of Kaplan-Meier.

The overall response rate at day 100 post ASCT will be estimated by the number of patients with an objective status of sCR, CR, VGPR, or PR at the day 100 post ASCT assessment divided by the total number of evaluable patients. Response assessment will be in comparison to values obtained at the disease assessment at the time registration. Exact binomial 95% confidence intervals for the true overall response rate at day 100 post ASCT will be calculated.

**Adverse Events:** All eligible patients that have initiated treatment will be considered evaluable for assessing adverse event rate(s). The maximum grade for each type of adverse event will be recorded for each patient, and frequency tables will be reviewed to determine patterns. Additionally, the relationship of the adverse event(s) to the study treatment will be taken into consideration.

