### 2.2 Secondary Objectives:

- 2.21 To determine percentage of patients achieving MRD negativity by MPF after 1 year of daratumumab+lenalidomide-based maintenance therapy.
- 2.22 To determine progression-free survival (PFS) for peri-SCT treatment with daratumumab.
- 2.23 To determine percentage of MRD negativity by MPF after pre-SCT consolidation with daratumumab.
- 2.24 To determine safety profile of peri-SCT daratumumab with lenalidomide.
- 2.25 To determine the overall response rate (ORR) of patients receiving peri-SCT daratumumab for MM.
- 2.26 To determine the overall survival (OS) for patients receiving peri-SCT daratumumab for MM.

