#### 13.5 Ineligibles

A patient is deemed *ineligible* if after registration, it is determined that at the time of registration, the patient did not satisfy each and every eligibility criteria for study entry. The patient may continue treatment off-protocol at the discretion of the physician as long as there are no safety concerns, and the patient was properly registered. The patient will go directly to the event-monitoring phase of the study (or off study, if applicable).

- If the patient received treatment, all data up until the point of confirmation of ineligibility must be submitted. Event monitoring will be required per the protocol.
- If the patient never received treatment, on-study material and the End of Active Treatment/Cancel Notification Form must be submitted. No further data submission is necessary.

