#### 16.52 Adverse Event Stopping Rules:

The stopping rules specified below are based on the knowledge available at study development. We note that the Adverse Event Stopping Rule may be adjusted in the event of either (1) the study re-opening to accrual or (2) at any time during the conduct of the trial and in consideration of newly acquired information regarding the adverse event profile of the treatment(s) under investigation. The study team may choose to suspend accrual because of unexpected adverse event profiles that have not crossed the specified rule below.

Accrual will be temporarily suspended to this study if at any time we observe events considered at least possibly related to study treatment (i.e. an adverse event with attribute specified as “possible,” “probable,” or “definite”) that satisfy one of the following:

- If 5 or more patients in the first 15 treated patients experience a grade 4 or higher non-hematologic adverse event at least possibly related to treatment.
- If after the first 15 patients have been treated, 30% of all patients experience a grade 4 or higher non-hematologic adverse event at least possibly related to treatment.

We note that we will review grade 4 and 5 adverse events deemed “unrelated” or “unlikely to be related”, to verify their attribution and to monitor the emergence of a previously unrecognized treatment-related adverse event.

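### Reported adverse event rates leave out patients who were dosed and later found ineligible, although their data are collected and the stopping rule carries no eligibility condition

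*Combined protocol and SAP*

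**What the plan says.** Section 16.42, under Adverse Events, defines the reporting population: "All eligible patients that have initiated treatment will be considered evaluable for assessing adverse event rate(s". Each patient then contributes the maximum grade for each type of event to frequency tables. These tables serve secondary objective 2.24: "To determine safety profile of peri-SCT daratumumab with lenalidomide".

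Section 13.5 defines an ineligible patient as one for whom, after registration, "it is determined that at the time of registration, the patient did not satisfy each and every eligibility criteria for study entry". It foresees that the patient may already have been dosed: "If the patient received treatment, all data up until the point of confirmation of ineligibility must be submitted". The patient then goes to event monitoring, or off study if applicable, and may continue treatment off protocol.

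The adverse event stopping rules in Section 16.52 use a different population. The first reads "If 5 or more patients in the first 15 treated patients experience a grade 4 or higher non-hematologic adverse event" and the second "If after the first 15 patients have been treated, 30% of all patients experience a grade 4 or higher non-hematologic adverse event". Neither mentions eligibility.

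On numbers, Section 16.12 states "A minimum of 20 and a maximum of 45 evaluable patients will be accrued total onto this phase II study" and adds "We anticipate accruing an additional 5 patients to account for ineligibility, cancellation, major treatment violation, or other reasons", for a total of 50.

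**The concern.** A safety rate normally describes everyone exposed to the treatment. In Section 16.42 the word *eligible* has only one practical effect. Patients who never started are already removed by the requirement to have initiated treatment, and major violations (Section 13.6) are not excluded from this set. What remains to be removed is the patient who was dosed and later failed an eligibility check. The efficacy set in Sections 16.11 and 16.411 also requires eligibility, which can be defended for a response rate in a target population. The plan gives no reason to carry that restriction over to safety, and no other section defines an all-treated safety set.

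The result is a mismatch within the plan. A treated patient's related grade 4 event can count towards suspending accrual and then be absent from the published table. With at most 45 evaluable patients, single patients move the rates visibly.

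**Working it through.** **The plan's own figure.** 45 evaluable + 5 allowance = 50 (Section 16.12), which agrees with the total of 50 in the accrual table of Section 16.7. No stated figure is wrong; the point concerns a population definition.

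**Inputs.** Eligible treated patients: 45, the maximum evaluable number. Treated patients later found ineligible: *k*, which the documents do not give. I take *k* = 1 to 5 as an assumption, bounded by the allowance of five.

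**Share of treated patients omitted** = *k* / (45 + *k*):

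| *k* | Treated | Omitted |
|---|---|---|
| 1 | 46 | 2.2% |
| 2 | 47 | 4.3% |
| 3 | 48 | 6.3% |
| 4 | 49 | 8.2% |
| 5 | 50 | 10.0% |

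This treats any unused part of the allowance as never-treated patients. If the unused places went to treated major violations instead, who stay in the adverse event set, the share would be *k*/50: 2.0% for one patient and 4.0% for two. The difference is negligible.

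**Effect on a reported rate.** With *x* events among 45 eligible patients, the all-treated rate lies between *x*/(45 + *k*), when none of the added patients has the event, and (*x* + *k*)/(45 + *k*), when all do. Take *x* = 9, a reported rate of 9/45 = 20%, for illustration:

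- *k* = 1: from 9/46 = 19.6% to 10/46 = 21.7%.
- *k* = 5: from 9/50 = 18% to 14/50 = 28%.
- *k* = 5 with the same 20% rate in the added patients (1 of 5): 10/50 = 20%, no change.

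For an event not seen in any eligible patient (0/45), the all-treated rate with *k* = 5 could be as high as 5/50 = 10%.

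**Chance of seeing an uncommon event at all.** For an event with a true rate of 2%, the chance of at least one case is 1 − 0.98^45 = 0.597 with 45 patients and 1 − 0.98^50 = 0.636 with 50. The gain is small even at the upper bound.

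**Mismatch with the monitoring rule.** Suppose 13 of 45 eligible patients and one treated ineligible patient have a qualifying event. The table shows 13/45 = 28.9%, below the 30% in Section 16.52. The all-treated figure is 14/46 = 30.4%, above it. The suspension rule would operate correctly, but the published table would not show the rate that triggered it.

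**The case against.** The strongest case on the other side is that the effect is small, unsigned and confined to descriptive tables. Most of that stands.

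- **Direction.** A reader might infer that dropping these patients makes the regimen look safer, since many entry criteria concern organ function, infection or cardiac history. The documents do not support that. Section 13.5 makes a patient ineligible for missing any criterion, including testing windows and measurable disease at a historical time point, which are not evident toxicity risks. Full data are also required only until ineligibility is confirmed. The event monitoring in Section 4.2 then tracks progression, subsequent therapy, death and new primaries, with limited late-event capture under the Section 4.1 footnotes. Patients removed early may therefore have few recorded events and could lower the rate.
- **Number.** A reader might also take 10% as the expected loss. It is only a ceiling under the plan: cancelled patients are never treated (Section 13.7), major violations remain in the adverse event set, and eligibility is verified at registration (Section 6.12). The true number may be very small.
- **Participant protection.** A reader might infer that safety oversight is weakened. It is not. The stopping rule, serious adverse event reporting (Section 10.41), routine reporting of grade 3 and 4 events (Section 10.62) and the twice-yearly monitoring board review (Section 16.51) carry no eligibility condition.
- **Relevance to the combination.** Lenalidomide starts only with maintenance (Section 7.13), so a patient found ineligible during the first consolidation adds information on daratumumab alone.

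These points limit the size of the problem. None of them is a reason to leave exposed patients out of the tables when their data have been submitted.

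**Conclusion.** The point holds as a gap in the safety reporting population. As written, Section 16.42 excludes dosed patients later found ineligible from the rates that answer objective 2.24, although Section 13.5 obtains their data up to confirmation and Section 16.52 applies no eligibility condition. The omission is at most 5 of 50 treated patients (10%) under the plan's allowance, and 2.2% or 4.3% if one or two patients are affected. These figures assume full accrual of 45 evaluable patients, and the number of treated ineligible patients is itself an assumption. The effect on any rate can go either way; the 18% to 28% range around 20% is the extreme case with five such patients. No decision rule, test or expedited report depends on it. It is a cheap improvement to the reporting, not a flaw in the design or in participant protection.

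**What to change.** In Section 16.42, replace the sentence that defines who is evaluable for adverse events with: *All patients who received at least one dose of study treatment, regardless of eligibility, will be evaluable for adverse events; for patients found ineligible, events reported up to confirmation of ineligibility are counted.*

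Leave the efficacy set in Sections 16.11 and 16.411 unchanged. An eligible-only adverse event table may be shown as a sensitivity analysis, with the number of treated ineligible patients stated.

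The cost is one sentence in the analysis plan and possibly one extra table. No patients, visits or tests are added, and the data are already required by Section 13.5. The small downside is that adverse event follow-up in these few patients is cut short at confirmation of ineligibility, which a footnote to the table should say.
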